5.2 Treatment arms

Patients will be randomized to the following three cohorts in a ratio of 1:1:1. Blinding will be done within each cohort. Patients will be further randomized within each cohort to one of the three treatment arms: TIP, TIP/placebo cyclical, or placebo with a randomization ratio of 2:2:1.

Cohort A:

- TIP: Three capsules of blinded TIP at 28 mg dosage strength, inhaled o.d. via the T-326 Inhaler, for 112 days (on treatment). The total daily dose and each treatment therefore consists of 84 mg tobramycin (3 capsules of 28 mg each),
- TIP/placebo cyclical: patients will take same doses, i.e. 3 capsules o.d., by alternating TIP 28-days with placebo 28-days for two cycles for a total of 112 days.
- Placebo: The reference product consists of placebo capsules (DSPC/CaCl₂). The dose regimen for the reference product is three capsules blinded, inhaled o.d. via the T-326 Inhaler, for 112 days (on treatment).

Cohort B:

- TIP: Five capsules of blinded TIP at 28 mg dosage strength, inhaled o.d. via the T-326 Inhaler, for 112 days (on treatment). The total daily dose and each treatment therefore consists of 140 mg tobramycin (5 capsules of 28 mg each).
- TIP/placebo cyclical: patients will take same doses, i.e. 5 capsules o.d., by alternating TIP 28-days with placebo 28-days for two cycles for a total of 112 days.
- Placebo: The reference product consists of placebo capsules. The dose regimen for the reference product is five capsules blinded, inhaled o.d. via the T-326 Inhaler, for 112 days (on treatment).

Cohort C:

- TIP: Four capsules of blinded TIP at 28 mg dosage strength, inhaled b.i.d. in the morning and in the evening via the T-326 Inhaler, for 112 days of treatment. Each dose therefore consists of 112 mg tobramycin (4 capsules of 28 mg each), the total daily dose corresponds to 224 mg tobramycin (112 mg b.i.d.),
- TIP/placebo cyclical: patients will take same doses, i.e. 4 capsules b.i.d., by alternating TIP 28-days with placebo 28-days for two cycles for a total of 112 days.
- Placebo: The reference product consists of placebo capsules. The dose regimen for the reference product is four capsules blinded, inhaled b.i.d. via the T-326 Inhaler, for 112 days (on treatment).

The treatment epoch is followed by a 56-day follow-up epoch (no study treatment).

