5.5.4 Instructions for prescribing and taking study treatment

The study drug (TIP or placebo) will be dispensed by the ISC at Visit 101 (start of treatment) and Visit 103 through Visit 106. Each patient will receive a kit of investigational treatment containing the medication for 28 days of treatment. For dosing visits 103, 104 and 105 study drug administered during the visit should be taken from the newly dispensed kit. At Visit 106, the study drug administered during the visit should be taken from the kit dispensed at Visit 105. Each kit contains five weekly boxes with each weekly box containing an inhaler and the required number of blister cards for one week dosing. The content of the fifth weekly box serves as a reserve in case a reserve inhaler is needed and provides supply until the next scheduled visit. Instructions for use for the T-326 Inhaler are given in [Appendix 4](#) and will be handed out to the patient at Visit 101. Use of the reserve supply will be recorded on the appropriate CRF.

Patients will be provided with medication as described in [Section 5.2](#).

The ISC will train the patient and assist and supervise the patient with the first inhalation at the site during Visit 101 by using instructions for use of T-326 Inhaler, describing in detail how to handle the drug-device combination. The ISC will also assist and supervise the patient's inhalation of the study drug at Visit 102 (Day 8) through Visit 106 (Day 113) or at the study treatment discontinuation visit (TD) if applicable. Detailed instructions for use are included in [Appendix 4](#). In summary, each capsule containing the study medication has to be removed one at a time from the blister card, inserted into the T-326 Inhaler, the inhaler actuated and the study drug inhaled according to instructions. Patients are instructed to perform two inhalations and breath-hold maneuvers for each capsule by default, then verify that the capsule has been emptied completely and inhale again as necessary.

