1. QOL-B, [REDACTED]

^m Identical training regardless of treatment arm.

ⁿ The ISC will assist subjects in conducting the first study drug inhalation (Visit 101), while the inhalation of the study drug at Visits 102, 103, 104, 105 and 106 (last study drug inhalation) at the study site is performed by the subject in the presence of the ISC.

^o If a patient prematurely discontinues study drug, study drug administration in the presence of the ISC, study drug accountability, post-dose spirometry and post-inhalation events should be assessed at the TD visit provided the patient agrees to inhale study medication during the visit.

^o Exit interviews should be conducted by telephone at the last follow-up visit after completion of the PRO questionnaires and preferably prior to other assessments. Approximately 25 patients are planned to be recruited.

^p Patients with a past history of clinically significant hearing loss in the opinion of the investigator and patients with primary ciliary dyskinesia (PCD) may be eligible only if their hearing threshold at screening audiometry is 25dB or lower at frequencies 0.5-4 kHz.

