- **Placebo:** The reference product consists of placebo capsules. The dose regimen for the reference product is 4 capsules blinded, inhaled b.i.d. via the T-326 Inhaler, for 112 days (on treatment).

There will be 3 study epochs with a total of 9 visits ([Figure 1](#)):

- Screening: up to 28 days with 1 clinic visit
- Double-blind treatment (within cohort): 112 days with 6 clinic visits [Visit 101 (Day 1), Visit 102 (Day 8), Visit 103 (Day 29), Visit 104 (Day 57), Visit 105 (Day 85) and Visit 106 or study treatment discontinuation (TD) (Day 113)]
- Follow-up: 56 days with 2 clinic visits [Follow-up Visit 201 (Day 141) and Follow-up Visit 202 or premature subject/patient discontinuation (PSD) (Day 169)]

The total duration of the study is expected to be up to 196 days. Patients will be assessed for safety, tolerability and efficacy (see protocol [[Table 6-1 – Assessment schedule](#)]).

Figure 1 Study design

The primary efficacy endpoint is the absolute change from baseline to Day 29 of treatment in the bacterial load in sputum in log₁₀ colony forming units (CFUs) of *P. aeruginosa*. Baseline is defined as the last measurement prior to the first dose of blinded study drug.

No interim analysis for efficacy is planned. There is an independent data monitoring committee (DMC) assigned to monitor the safety during the study; further details are defined in the DMC Charter.

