1.2.3 Exploratory objectives

- To explore the characteristics of the post-inhalational events at all visits during the treatment epoch.

[figure not shown]
[figure not shown]
[figure not shown]

[figure not shown]
[figure not shown]
[figure not shown]

- To explore the impact of healthcare resource utilization of TIP treatment.

Table 1-2 Exploratory objectives and related endpoints

Objective	Endpoint	Statistical Analysis

Objective	Endpoint	Statistical Analysis
		
To explore the characteristics of the post-inhalational events	Separate summaries for post-inhalation clinical events and post-inhalation adverse events: Proportion of patients experiencing events at each visit Proportion of patients experiencing events that are ongoing at the completion of the visit Proportion of patients experiencing events with an action taken to reduce the event Time of onset of event Duration of event Number of post-inhalation events Event rate adjusted for exposure	2.7.4.3
		
To explore the impact of healthcare resource utilization of TIP treatment	All scheduled and unscheduled visits	2.7.4.5
		

2 Statistical methods

The study is characterized by 3 cohorts (corresponding to 3 doses). Each cohort consists of TIP, TIP/placebo cyclical, or placebo in a ratio of 2:2:1. Data will be summarized and analyzed by cohort/dose, treatment arms (including combined treatments) and/or pooled by continuous, cyclic and placebo as appropriate. For the efficacy analyses, the placebo patients will be pooled from the 3 cohorts.

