2.1.1 General definitions

Study drug is defined as any single dose of TIP or placebo administered to the patient as part of the required study procedures.

The date of first dose of study drug is defined as the date of first administration of TIP or placebo; the date of last dose of study drug is defined as the date of the last administration of TIP or placebo.

For dates on or after the date of first dose of study drug, study day is defined as [date of interest – date of first dose of study drug] + 1. For dates before the date of first dose of study drug, study day is defined as [date of first study drug – date of interest].

For each visit, the date recorded by the investigators in the eCRF (variable SVSTDTC in the SDTM SV dataset) will be considered as the visit date in all the algorithms and the listings.

In general, the nominal visits will be used for the by visits summaries. However, for early treatment discontinued patients, data collected at end of treatment (EOT) visit will be mapped to next planned visits after their last scheduled visits before the discontinuation.

Baseline is defined as the last non-missing result prior to the first administration of study drug.

End/last date of study for each patient is defined by the date of last contact as recorded in the database.

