2.7.4.3 Post-inhalation events

Events occurring within 5 minutes after inhalation of the study treatment (post-inhalation events) will be observed at the site by site personnel at Visit 101 (start of treatment), Visit 102 (Day 8), Visit 103 (Day 29), Visit 104 (Day 57), Visit 105 (Day 85) and Visit 106 or TD (Day 113). If the event is determined to be an adverse event, this should be recorded on the Adverse Event eCRF. In addition, event details will also be captured in the Post-inhalation Adverse Event eCRF. For post-inhalation events that are determined not to be an adverse event, event details will be recorded in the Post-inhalation clinical events eCRF.

A separate PK sub-study is included in this study which collects additional PK samples. Patients included in this sub-study will provide 1 serum specimen per specified interval at Visit 101 (start of treatment) and Visit 103 (Day 29): pre-dose, 0-1, 1-2, 3-4 and 5-6 h. Descriptive statistics (n, mean, SD, minimum, median and maximum) will be provided for the PSSAS by scheduled visit and time point.

All PK data will be presented in individual patient data listings.

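### In the cyclical arms, the SAP's visit-mapping rule files post-dose results from some early-discontinuation visits under a visit where the arm inhales the opposite capsule

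*SAP*

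**What the plan says.** SAP 2.1.1 sets the rule for tables by visit: "In general, the nominal visits will be used for the by visits summaries". For early stoppers it adds that "data collected at end of treatment (EOT) visit will be mapped to next planned visits after their last scheduled visits before the discontinuation".

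The cyclical patients take their capsules "by alternating TIP 28-days with placebo 28-days for two cycles for a total of 112 days" (Protocol 5.2). On the source of the dose taken at the site, Protocol 5.5.4 says: "For dosing visits 103, 104 and 105 study drug administered during the visit should be taken from the newly dispensed kit". The same section takes the Visit 106 dose from the kit issued at Visit 105.

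Dose-linked results are collected at the TD visit. A footnote to Protocol Table 6-1 says that "post-dose spirometry and post-inhalation events should be assessed at the TD visit provided the patient agrees to inhale study medication during the visit". Both data types feed summaries organised by visit. SAP Table 1-2 lists "Proportion of patients experiencing events at each visit" among the post-inhalation endpoints (exploratory), and SAP Table 1-1 lists acute FEV1 change from pre-dose to about 30 minutes post-dose at treatment visits (secondary). Protocol 9.5.2 also summarises several characteristics of post-inhalation events for each cycle.

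**The concern.** Slotting a TD visit into the next planned visit is reasonable for measurements that reflect the preceding weeks. It is not neutral for a reaction seen minutes after an inhalation. In the continuous and placebo arms the capsule never changes, so the slot does not matter. In the cyclical arms the content changes at exactly the visits to which most TD data would be moved. A reaction to TIP could appear in a row where the rest of the arm inhaled placebo, and a placebo result in a row where they inhaled TIP.

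At stake is how the cyclical rows are read in two descriptive safety displays. The arms are small and only the cyclical arms are exposed to the problem, so a single misplaced event can show in a comparison of cyclical with continuous dosing at that visit. The SAP already treats the visit periods as on and off phases of the cyclical arms when it assesses compliance (SAP 2.4.1), but gives post-dose data no similar protection.

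**Working it through.** The plan states no figure on this point, so there is none to reproduce. The check lists each possible stopping interval and compares two capsules.

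**Inputs.**
- Visit days: "Visit 101 (Day 1), Visit 102 (Day 8), Visit 103 (Day 29), Visit 104 (Day 57), Visit 105 (Day 85"), then Visit 106 on Day 113 (SAP 1.1).
- On-site dose in a cyclical arm: Visits 101 and 102 use the first kit (TIP). Visit 103 uses the new kit (placebo), Visit 104 the new kit (TIP) and Visit 105 the new kit (placebo). Visit 106 uses the Visit 105 kit (placebo).
- TD dose: assumed to come from the kit in use. No passage names the kit for a TD visit.
- All earlier visits are assumed attended, and the TD visit is assumed to precede the next planned visit day.

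**Comparison by interval.**

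| Last visit attended | Mapped to | Capsule at TD | Capsule at mapped visit | Result | Days |
|---|---|---|---|---|---|
| 101 | 102 | TIP | TIP | same | 8 − 1 = 7 |
| 102 | 103 | TIP | placebo | opposite | 29 − 8 = 21 |
| 103 | 104 | placebo | TIP | opposite | 57 − 29 = 28 |
| 104 | 105 | TIP | placebo | opposite | 85 − 57 = 28 |
| 105 | 106 | placebo | placebo | same | 113 − 85 = 28 |

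**Share of treatment time.** Opposite: 21 + 28 + 28 = 77 days. Total: 112 days. 77/112 = 68.75%. Same: 7 + 28 = 35 days, 31.25%.

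**Number of patients.** Let d be the proportion stopping early and p the proportion of those who accept the TD dose. With 2:2:1 allocation and stops spread evenly over 112 days:

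N = 107 × 2/5 × d × 77/112 × p

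107 × 2/5 = 42.8 cyclical patients, or about 14 per cohort. At d = 20%, 42.8 × 0.20 = 8.6 stop early, and 8.56 × 0.6875 = 5.9 fall in a mismatched interval.

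| d | p = 0 | p = 0.5 | p = 1 |
|---|---|---|---|
| 10% | 0 | 1.5 | 2.9 |
| 20% | 0 | 2.9 | 5.9 |
| 30% | 0 | 4.4 | 8.8 |

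**Size per table row.** At d = 20% and p = 1, the expected count per cohort mapped to Visit 103 is 8.56 × 21/112 ÷ 3 = 0.5. For Visits 104 and 105 it is 8.56 × 28/112 ÷ 3 = 0.7 each. These are patients with misplaced data, not events. If one of them does react, the event moves a row of 14 by 1/14, about 7 percentage points.

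**By cycle.** Only stops after Visit 103 can also change cycle. A placebo dose from cycle 1 would be mapped to Visit 104, the first TIP dose of cycle 2, if cycle is derived from the mapped visit.

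**The case against.** The strongest reply is that little of importance is affected, and most of that reply stands.

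**Primary objective.** A reader might infer that the primary tolerability objective is compromised. The documents do not support this. Its endpoint is the incidence and severity of local adverse events. SAP 2.7.1 counts these from first dose to study completion by system organ class, preferred term and maximum severity, not by visit. A post-inhalation event judged to be an adverse event also goes on the adverse event form, so it is counted there whatever its visit slot. Listings are ordered by assessment date (SAP 2.1.3), and safety is descriptive, without testing (SAP 2.7).

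**Internal contradiction.** SAP 2.7.4.3 lists the last assessment as "Visit 106 or TD (Day 113"), and the laboratory, vital-sign and QOL-B sections label it in the same way. One might read this as contradicting 2.1.1. Those sentences describe when data are collected, while 2.1.1 says where they are tabulated. Both can hold.

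**Vital signs.** One might also infer that TD vital signs land at visits with no scheduled vital signs. That follows only if the next planned visit means a visit of any kind. Read per assessment, they stay with Visit 106.

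**Acceptance of the TD dose.** TD dose data exist only if a patient who has stopped the drug agrees to inhale again. Those who reacted may be the least willing, so 5.9 is a ceiling at 20% stopping and the floor is zero. The 20% comes from the sample size section, for a Day 29 endpoint, and has no stated time horizon.

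**An exception elsewhere.** The rule opens with a general qualifier. In the copy reviewed, SAP 2.7.4.3 breaks off after describing data capture and 2.7.4.4 is absent. A local TD rule for these two analyses cannot be excluded.

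None of this removes the mismatch for TD visits mapped to Visits 103, 104 and 105.

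**Conclusion.** The point holds within limits. As far as the available text shows, SAP 2.1.1 places TD post-dose results under the opposite capsule in the cyclical arms when the last attended visit is 102, 103 or 104. It would be too broad to say this of every TD visit: two of the five intervals match.

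The 69% is a share of treatment time. It equals the share of early stops only if stops are evenly spread. The patient count rests on the 2:2:1 split among the 107 randomised, a 20% stopping rate and the kit-in-use assumption. It runs from zero to about six across the three cyclical arms at that rate, or about nine at 30% stopping with full acceptance.

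The consequence is mislabelled rows in one secondary and one exploratory descriptive summary. The capsule phase of pre-dose CFU is not affected, because the sample at the next visit is taken before the new kit is used and so reflects the same phase. The issue is modest in size, but it comes from a stated rule and is worth correcting because the correction is cheap.

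**What to change.** In SAP 2.1.1, keep the mapping for data that are not dose-linked (CFU, QOL-B, laboratory, audiology), so that those TD values still have a slot. Exclude post-inhalation events and pre-/post-dose FEV1 from it. Show their TD results in a separate TD row, classified by the content of the kit actually inhaled (TIP or placebo, from the IRT records) and by the cycle in which the dose was taken. Cross-refer to SAP 2.7.4.3 and 2.7.4.4, and align the wording with any TD rule already there.

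The cost is a few sentences and one programming flag. Protocol 5.5.4 already has all assigned kits recorded in the IRT, so no new data are needed. The small downside is that a few TD values leave the by-visit rows.

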2.1.2 Statistical significance

The step-wise Dunnett procedure will be used for the primary efficacy analysis to control the family-wise type-I error rate (3 dose levels versus placebo) at the 2-sided 5% significance level (Section 2.5.2). Unless otherwise specified, other inferential analyses and confidence intervals (CIs) will be conducted at the 2-sided 5% significance level with no multiplicity adjustment.

2.1.3 Listings

All data collected in the eCRF and diaries will be presented in the listings.

Data will be presented in listings in the order of cohort [Cohort A: 3 capsules OD, Cohort B: 5 capsules OD and Cohort C: 4 capsules BID], treatment arm [TIP, TIP/Placebo Cyclical and Placebo], site/patient identifier, assessment date and assessment (in order collected in the eCRF, unless specified otherwise). AE listings will include the AE start day and AE stop day relative to the first day of study drug. Dates will be presented in format DDMMYYYY.

2.2 Analysis sets

Safety Set (SAF): The safety set will be used for all safety analyses, which is defined as patients who received at least 1 dose of study drug. Patients will be analyzed according to the actual treatment received.

For the purposes of tables and listings a further 3 populations are defined:

- All enrolled patients (ENR)
- Screening failure patients
- Randomized population (RAN: all randomized patients)

Full Analysis Set (FAS): The full analysis set (FAS) will include all randomized patients who received at least 1 dose of study drug. Following the intent-to-treat principle, patients will be analyzed according to the treatment they are assigned to at randomization, which may be different from the actual treatment received. Patients who are mistakenly randomized or who have not taken double blind study drug will be excluded from the FAS. This is the primary analysis set for all efficacy analyses.

Per-Protocol Set (PPS): The per-protocol set (PPS) will include all patients in the FAS without any major protocol deviations.

Criteria for determining protocol deviations will be defined and documented in the protocol deviations section of the data validation specifications. Potential protocol deviators will be identified and reviewed to determine whether they will be excluded from the PPS population. This will take place in a blinded data review meeting prior to database lock. All protocol deviations will be agreed and documented prior to unblinding the study. The PPS will be used for the supportive analysis of the primary efficacy variable.

Pharmacokinetic Analysis Set (PKAS): The pharmacokinetic analysis set (PKAS) will include all patients who are administered TIP, and for whom results of plasma concentrations are obtained for at least one sampling point during the study.

Pharmacokinetic Sub-study Analysis Set (PKSSAS): The pharmacokinetic sub-study analysis set (PKSSAS) will include all patients enrolled in the pharmacokinetic sub-study

who are administered TIP, and for whom results of plasma concentrations are obtained for at least one sampling point during the study.

Audiology Population (AUD): The audiology population is defined as all patients in the safety set with at least one audiology test performed.

